### **Efficacy Measures**

10. CMV Infection (Secondary Outcome) – defined as detectable CMV in the patient's plasma. Currently, MUSC uses CMV DNA PCR (plasma IU/mL) to assess for infection with nucleic acid amplification techniques that are calibrated to the WHO international standard for human CMV. The lower level of detection is 50 IU/mL. Per the MUSC CMV protocol and usual care (see Appendix), any level >1,000 IU/mL will be considered CMV infection for the purposes of this study. All cases of CMV infection, regardless of the presence or absence of symptoms, will be classified as infection. CMV DNA PCR is measured at MUSC per our protocol using event-driven criteria, which includes either leukopenia or symptoms consistent with CMV infection (N/V/D, anorexia, fever, chills, and/or malaise). For the purposes of this study, the reason for measuring CMV DNA PCR will be captured and analyzed as well. Further, MUSC usual care CMV protocol suggests measuring CMV DNA PCR in those that are D+/R- after prophylaxis is discontinued (post-transplant month 7, 9 and 12). The protocol also recommends measuring CMV DNA PCR at month 4, 7, and 12 after discontinuation of antiviral prophylaxis in moderate risk patients (R+, see Appendix). CMV symptoms and treatment will also be recorded. Late CMV infection will be defined based on occurrence of first CMV infection after completion of CMV prophylaxis (3- or 6-months post-transplant). These endpoints will be assessed at 3-, 6-, and 12-months post-transplant. Breakthrough cases of CMV infection, defined as the presence of CMV DNA while on anti-CMV prophylaxis, will also be assessed.
11. CMV Disease (Secondary Outcome) – defined as the presence of organ dysfunction in the setting of CMV infection with biopsy proven presence of CMV in the affected organ, done at MUSC using DNA hybridization. This will be sub-classified by organ type; most common in kidney transplant recipients will be CMV gastrointestinal disease, CMV pneumonia, or CMV nephritis. Less common include CMV hepatitis, CMV retinitis, CMV encephalitis, CMV cystitis, CMV myocarditis, and CMV pancreatitis. Late CMV disease will be defined based on occurrence of first CMV infection after completion of CMV prophylaxis (3- or 6-months post-transplant). This endpoint will be assessed at 3-, 6-, and 12-months post-transplant. Breakthrough cases of CMV disease will also be assessed.

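### CMV disease depends on a CMV infection criterion that item 10 words in conflicting ways, so tissue-proven disease with low or no viremia can go uncounted

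*Combined protocol and SAP*

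**What the plan says.** Both definitions are in the combined protocol and SAP, section 4.0, Efficacy Measures.

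- **Item 10, CMV infection.** The first sentence reads "defined as detectable CMV in the patient's plasma". The item then states "The lower level of detection is 50 IU/mL" and, shortly after, "any level >1,000 IU/mL will be considered CMV infection for the purposes of this study". Breakthrough infection has a third wording with no threshold: "defined as the presence of CMV DNA while on anti-CMV prophylaxis".
- **Item 11, CMV disease.** It is "defined as the presence of organ dysfunction in the setting of CMV infection with biopsy proven presence of CMV in the affected organ", with the tissue work "done at MUSC using DNA hybridization". Cases are sub-classified by organ. After three common sites the item adds: "Less common include CMV hepatitis, CMV retinitis, CMV encephalitis, CMV cystitis, CMV myocarditis, and CMV pancreatitis". It gives no other route to confirmation and no step for classifying unclear cases.

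Both are secondary outcomes. They serve Aim 2, whose hypothesis (section 1.0) is that infection and disease will occur at similar rates in the two arms at 3, 6 and 12 months.

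**The concern.** Item 11 requires three things together: organ dysfunction, CMV infection, and CMV in a biopsy of that organ. The second carries whatever meaning item 10 gives it, and item 10 gives more than one. Two problems follow.

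First, one patient can be scored in two ways. Treatment assignment is known, so a choice of wording made after events have accrued could be influenced by the arm the patient is in.

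Second, the stated study rule lets a blood level override a positive tissue finding. Disease is the most clinically serious efficacy outcome in Aim 2, and where few events are expected each reclassified case moves the estimate visibly.

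**Working it through.** **No plan figure to reproduce.** The documents give no expected rate, power or margin for CMV disease in this trial. The check is a reading of the definitions, followed by arithmetic on assumed rates.

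**1. Apply both wordings to a patient with organ dysfunction and CMV-positive tissue.**

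| Plasma CMV | Infection means detectable | Infection means above 1,000 IU/mL |
|---|---|---|
| Above 1,000 IU/mL | Disease | Disease |
| 50 to 1,000 IU/mL | Disease | Not disease |
| Undetectable | Not disease | Not disease |

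A patient with a positive colon biopsy and 600 IU/mL falls in the middle row. The two wordings disagree there, and item 11 does not settle it. In the bottom row they agree that a tissue-proven case is not counted.

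Without tissue, no case counts on either wording, whatever the site or viral load.

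**2. Compare with the plan's handling of BK virus.** Item 14 defines BK nephropathy from the biopsy pathology report and states no viremia condition for it. The plan gives no reason for treating CMV tissue findings differently.

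**3. Size of one case.** 1/35 = 0.0286, or 2.9 percentage points of an arm.

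**4. Expected counts per arm.** Formula: 35 × p × s, where p is the true 12-month disease rate and s the share of true cases that the definition captures. The value p = 16.1% is the Background figure for D+/R- patients on 200 days of valganciclovir. It serves only as an upper guide, because this trial also enrols rATG recipients of other serostatus. The values 10% and 5%, and every s below 1, are assumptions.

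| p | s = 1 | s = 0.90 | s = 0.75 | s = 0.50 |
|---|---|---|---|---|
| 16.1% | 5.6 | 5.1 | 4.2 | 2.8 |
| 10% | 3.5 | 3.2 | 2.6 | 1.8 |
| 5% | 1.8 | 1.6 | 1.3 | 0.9 |

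Lost cases, 35 × p × (1 − s), run from 35 × 0.05 × 0.10 = 0.2 to 35 × 0.161 × 0.50 = 2.8 per arm. This range only restates the assumed p and s; it is not an estimate.

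**5. Effect on the comparison.** If both arms lose the same share and no false cases are added, the difference becomes s × (p1 − p2), while the ratio stays at p1/p2. For example, take assumed true rates of 16.1% and 10% with s = 0.75:

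- Observed rates: 0.161 × 0.75 = 12.1% and 0.10 × 0.75 = 7.5%.
- Difference: 6.1 points becomes 4.6.
- Ratio: 1.61 both before and after.

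**6. Primary endpoint.** The Power/Sample Size section rests on leukopenia incidence alone. CMV disease does not enter it.

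**The case against.** The best defence is that a strict definition protects specificity in an open-label trial, and that CMV disease is a secondary outcome in a study which already disclaims power for CMV endpoints. That is fair as to severity. It also supports requiring tissue proof, which the change below keeps. It does not support adding a plasma condition to a case that tissue has already proven.

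It can also be said that such patients remain visible: CMV symptoms and treatment are recorded, and CMV admissions and ED visits are sub-analysed. True, but none of this puts them back into the disease count. Item 10 also refers to an appendix and item 11 cites published trial definitions. Neither can be consulted here, so any clarification they hold cannot be credited.

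A reader might infer more than the text supports in four ways:

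- **That 1,000 IU/mL is the only meaning of infection.** It is the only sentence framed as a study rule, but the detectable wording stands in the same item. Exclusion at 50 to 1,000 IU/mL is therefore one of two readings.
- **That retinitis and encephalitis are scored as no disease.** They are listed as disease sub-types and fail only if no tissue is taken. How often those sites are biopsied is not in the documents.
- **That cases are lost because no PCR is drawn.** Item 10 says "CMV DNA PCR is measured at MUSC per our protocol using event-driven criteria, which includes either leukopenia or symptoms consistent with CMV infection", and diarrhoea is among the symptoms it lists. A symptomatic patient without a PCR would be a departure from usual care, not a product of the definition.
- **That the rule favours one drug.** Leukopenia prompts PCR and is expected more often on valganciclovir, but symptoms prompt it too, and no figure shows unequal loss of disease cases. With equal loss the ratio is unchanged. Nothing in the documents says that either drug lowers plasma virus while leaving tissue infected.

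**Conclusion.** The point holds as a defect in an Aim 2 endpoint definition. Tissue-proven disease with undetectable plasma is missed on either wording. At 50 to 1,000 IU/mL it is missed or counted depending on which sentence of item 10 is applied. Uncounted cases pull the absolute difference toward zero, the direction in which a hypothesis of similar incidence is easiest to accept.

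The number of patients affected cannot be derived from the documents. It could be none; on the assumptions above it would be at most about three per arm. No claim is made about which arm would gain. The change is worth making because the rule is unclear on its face and easily repaired.

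**What to change.** Amend items 10 and 11 before outcomes are reviewed by arm:

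1. Define CMV disease as organ dysfunction with CMV shown by biopsy in the affected organ, whatever the plasma level.
2. Count every such case as a CMV infection as well, so that disease stays a subset of infection. Give it an event date, such as the biopsy date, because item 11 classes disease as late by when infection first occurs.
3. State one viremia threshold for CMV infection and use it throughout both items. If breakthrough infection is meant to use a different level, say so.
4. Keep the viremia-gated disease definition as a sensitivity analysis, using the same threshold.
5. Optionally, list by arm any case at a named site that was diagnosed without tissue, described separately and outside the main disease count.

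The first four steps cost only wording. Biopsy pathology reports and laboratory data are already collected, so no test or visit is added. A few tissue-positive cases with low or no viremia would enter the count, and the sensitivity analysis shows their effect. The optional listing brings in unblinded clinical judgement, which is why it should stay descriptive.

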12. Probable or Likely Refractory CMV Infection (Exploratory Outcome) – defined as a persistent viral load (CMV viral load at the same level or higher than the peak viral load within 1 week but <1 log 10 increase in CMV DNA titers done in the same laboratory and with the same assay) after at least 2 weeks of appropriately dosed anti-viral therapy.

13. CMV Antiviral Drug Resistance (Exploratory Outcome) – defined as a viral genetic alteration that decreases susceptibility to one or more antiviral drugs. This is a send out laboratory assessment at MUSC. All send out reports for patients in this study will be reviewed for possibility of resistance. We will capture and report the type of resistance in terms of the specific mutations and which agents are likely to incur resistance based on these gene variants.

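### The only refractory-CMV outcome stops at a rise below 1 log10, and no other endpoint captures a larger rise on treatment

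*Combined protocol and SAP*

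**What the plan says.** Section 4.0, Efficacy Measures, item 12 is titled "Probable or Likely Refractory CMV Infection (Exploratory Outcome"). It requires persistence of viral load, explained as "CMV viral load at the same level or higher than the peak viral load within 1 week", then bounded above by "but <1 log 10 increase in CMV DNA titers done in the same laboratory and with the same assay", and assessed "after at least 2 weeks of appropriately dosed anti-viral therapy".

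The neighbouring items measure other things:

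- Item 10, CMV infection, is a single-level threshold: "any level >1,000 IU/mL will be considered CMV infection for the purposes of this study". Its breakthrough sub-measure is "defined as the presence of CMV DNA while on anti-CMV prophylaxis".
- Item 11, CMV disease, needs "presence of organ dysfunction in the setting of CMV infection with biopsy proven presence of CMV in the affected organ".
- Item 13, antiviral resistance, is "defined as a viral genetic alteration that decreases susceptibility to one or more antiviral drugs", taken from send-out laboratory reports.

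The Statistical Methods do not mention refractory infection and add no further category.

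**The concern.** An outcome meant to describe failure to respond to antiviral treatment should not lose patients as the failure gets worse. Item 12 has a floor (at or above peak) and a ceiling (less than 1 log10 above), and nothing is defined above the ceiling. A load that stays flat on treatment is an event. A load that has risen 10-fold or more by the first qualifying sample is not.

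What is at stake is how a small exploratory table can be read. Its refractory row would omit some of the largest on-treatment rises, and a reader could not tell from the definition that they had been left out. The trial is also open-label. If the question is left open, someone will have to decide how to classify such a patient when the treatment arm is known.

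**Working it through.** The plan states no figure to reproduce here, so the check is to apply the rule and then look for another endpoint that covers what it omits.

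**Step 1: the rule.** From item 12, take d = log10(viral load on treatment ÷ peak viral load), after at least 2 weeks of appropriately dosed therapy. A patient is counted if 0 ≤ d < 1. This assumes that the 1 log10 rise is measured from the peak, which the text does not say outright.

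**Step 2: apply it.** The peak of 10,000 IU/mL is assumed for illustration.

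| On-treatment load (IU/mL) | d | Counted as written | Counted without the ceiling |
|---|---|---|---|
| 5,000 | −0.30 | no | no |
| 10,000 | 0.00 | yes | yes |
| 50,000 | +0.70 | yes | yes |
| 99,000 | +0.996 | yes | yes |
| 100,000 | +1.00 | no | yes |
| 300,000 | +1.48 | no | yes |
| 1,000,000 | +2.00 | no | yes |

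The rule depends only on the ratio to peak, so the pattern is the same for any peak. As the load rises, a patient goes from not counted, to counted, to not counted again.

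**Step 3: does another endpoint catch d ≥ 1?**

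- Item 10 counts the patient as infected above 1,000 IU/mL but has no criterion for change on treatment. Its breakthrough measure concerns viral DNA during prophylaxis, not response to treatment.
- Item 11 needs biopsy-proven organ involvement.
- Item 13 needs a genetic finding on a send-out report, whatever the viral load has done.
- The remaining items of section 4.0 and the Statistical Methods contain no such criterion. The Appendix, which is not in the supplied text, is cited in item 10 for the usual-care CMV protocol and not for endpoint definitions.

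**Step 4: sensitivity to what item 12 leaves unstated.**

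- *Which sample governs.* With a peak of 10,000, a patient at 50,000 on the first sample after week 2 (+0.70) qualifies then, even if a later sample is 300,000 (+1.48). A patient whose first such sample is already 300,000 does not qualify on it. The same eventual load gives two classifications, depending on when samples are taken.
- *Reference value.* Suppose the load was 5,000 at the start of treatment, the peak was 10,000, and the sample is 50,000. From the peak, d = log10(50,000 ÷ 10,000) = 0.70, counted. From the start, d = log10(50,000 ÷ 5,000) = 1.00, not counted. The one-week window attached to the peak is not tied to a calendar point either.

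**Step 5: size.** The documents give no rate of refractory CMV, so the number of patients affected cannot be computed.

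**The case against.** The strongest defence is the title. Item 12 calls itself probable or likely refractory infection, which names a tier and does not claim to cover all refractory infection. On that reading the ceiling may be right for its tier, and the fault is a missing upper tier. This stands, and it is why the fix keeps the existing wording. It does not remove the gap, because no upper tier is defined anywhere.

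It is also true that these patients are not lost. They remain in item 10, and in items 11 or 13 where those criteria are met. The outcome is exploratory, has no hypothesis attached, and section 10.0 already disclaims power for CMV infection.

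Three stronger readings are tempting, and the documents do not support them:

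- A reader might infer that every patient with a rise of 1 log10 or more is misclassified. A patient rising gradually could qualify at an earlier sample, as step 4 shows. Nor does item 12 assign anyone outside it to a non-refractory group.
- A reader might size the problem from the 17% late-infection rate in section 2.0: 0.17 × 35 = 5.95, about 6 per arm, so that one omitted patient looks like a sixth of the infections. The quoted interval of 2% to 29% gives 0.02 × 35 = 0.7 to 0.29 × 35 = 10.15 late infections per arm. Infections are in any case the wrong count, since item 12 also needs at least 2 weeks of treatment and non-response.
- A reader might infer that an arm with less susceptible virus would look better. Nothing in the documents links reduced susceptibility to rises of 1 log10 or more rather than to persistent loads, which item 12 does count. Breakthrough infection and resistance are also assessed separately.

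**Conclusion.** The concern holds as a minor defect in an endpoint definition. Item 12 counts a flat viral load on treatment and, as written, omits a patient whose first qualifying sample shows a 10-fold or greater rise, with no other item to capture that rise. The conclusion rests on the protocol's own wording and on reading the rise as measured from the peak. A different reference value would move the boundary but would not fill the gap above it.

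The number of patients affected cannot be estimated and may be small or zero. The primary outcome, the sample size and the power calculation are untouched. The documents support neither a claim of bias between arms nor any figure for the proportion of cases missed.

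**What to change.** In item 12:

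1. Keep the present probable-or-likely tier as it is.
2. Add a category for a rise of 1 log10 or more after at least 2 weeks of appropriately dosed therapy.
3. Report each category and their total by arm, so that the total includes every patient at or above peak. Item 14 already works this way for BK viremia: severe cases (at least 10,000 copies/mL) stay within the wider group (at least 2,000 copies/mL).
4. State the reference value for the rise, including what the one-week window refers to, and which sample governs when there are several (for example the first after 2 weeks, or the worst).

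The cost is a few lines of text. The classification uses PCR values already abstracted from the medical record and needs no extra visits or tests. It should be settled before outcome data are reviewed by arm.

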### **Additional Measures**

14. BK Infection (Exploratory Outcome) – defined as BK viremia of at least 2,000 copies/mL. Severe BK infection will be defined at BK viremia of at least 10,000 copies/mL. BK nephropathy will be defined based on the pathology report from the kidney allograft biopsy. The severity and duration of BK infection will be recorded for all patients.
15. Non-CMV, Non-BK Infections (Exploratory Outcome) – defined as any diagnosed and treated infection that leads to hospitalization, and will be sub-classified as bacterial, viral, or fungal etiologies. Opportunistic infections will also be sub-classified for this study as viral, bacterial, or fungal and defined as infections not seen in immunocompetent individuals. The study coordinator capturing clinical event data will review the medical record to determine the timing, severity, treatment regimen and cure time of each infection episode.
16. Healthcare Utilization (Secondary Outcome) – each encounter will be captured during the 12-month study and classified as hospitalizations, ED visits, ambulatory care visits, ambulatory care procedures, radiology encounters, telemedicine visits, telephone calls, and laboratory encounters. Only MUSC encounters will be captured. Data will be analyzed based on utilization type and provider type (Transplant vs. Other). Healthcare charges will be captured from MUSC hospital accounting. Charges will be converted to estimated costs using the Medicare Cost-to-Charge Ratio (CCR) for MUSC. This endpoint will be assessed at 3-, 6-, and 12-months post-transplant.
17. Health-Related Quality of Life (Exploratory Outcome) – the PROMIS QOL will be used to assess health-related quality of life. This questionnaire will be administered to patients at 3-, 6-, and 12-months post-transplant. Results will be compared between study arms.
18. Patient Satisfaction (Exploratory Outcome) – a validated survey provided by will be used to assess patient experience and satisfaction. This instrument will be administered at 3-, 6-, and 12-months post-transplant.

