## 1.0 Objectives / Specific Aims

- Aim 1. Assess the incidence of leukopenia in those randomized to maribavir vs. valganciclovir prophylaxis in adult kidney transplant recipients at high-risk of CMV infection.
  - Hypothesis 1. The incidence of clinically meaningful leukopenia, defined as a WBC count of  $< 3,000$  cells/mm^3 and a reduction in total mycophenolate dose below 1,500 mg/day or valganciclovir dose below 900mg per day (adjusted for renal function), will be significantly lower in the maribavir arm, as compared to the valganciclovir arm.
- Aim 2. Assess the efficacy of maribavir vs. valganciclovir prophylaxis in adult kidney transplant recipients at high-risk of CMV infection.
  - Hypothesis 2. The incidence of CMV infection and disease will be similar between the maribavir arm, as compared to the valganciclovir arm, at 3-, 6-, and 12-months post-transplant.
- Aim 3. Assess the impact of maribavir vs. valganciclovir prophylaxis on healthcare utilization and costs in adult kidney transplant recipients at high-risk of CMV infection.
  - Hypothesis 3. Healthcare utilization will be lower in the maribavir arm, as compared to the valganciclovir arm, at 6- and 12-months post-transplant, driven predominantly by reduced number of telephone calls, televisits, and laboratory monitoring encounters.
- Exploratory Aim 4. Assess the impact of maribavir vs. valganciclovir prophylaxis in adult kidney transplant recipients at high-risk of CMV infection on patient-reported outcomes for quality of life and satisfaction.
- Exploratory Aim 5. Assess any differences in leukopenia, efficacy, healthcare utilization and patient reported outcomes by race and sex in patients randomized to maribavir vs. valganciclovir prophylaxis in adult kidney transplant recipients at high-risk of CMV infection.

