### 4.0 Study Endpoints

#### Safety Measures

1. Leukopenia with an accompanying dose reduction (Primary Outcome) – Defined as a total WBC count of  $< 3,000$  cells/mm^3 with a reduction in the total daily dose of mycophenolate below 1500mg per day or valganciclovir below 900mg daily (adjusted for renal function). This will be assessed as a dichotomous outcome (yes/no) per patient as well as a rate (number of unique leukopenia events per patient-year). Events will be considered unique once the WBC count recovers to normal range on two consecutive measures. The length of time a patient has leukopenia, and the severity of leukopenia (nadir WBC) will also be assessed. This endpoint will be measured at 3-, 6-, and 12-months post-transplant.

2. Neutropenia (Secondary Outcome) – Defined as an absolute neutrophil count of  $<1,000$  cells/mm^3. This will be assessed as a dichotomous outcome (yes/no) per patient as well as a rate (number of unique neutropenic events per patient-year). Events will be considered unique once the neutrophil count recovers to normal range on two consecutive measures while not receiving G-CSF therapy. The length of time a patient has neutropenia, and the severity of leukopenia (nadir WBC) will also be assessed. This endpoint will be measures at 3-, 6-, and 12-months post-transplant.
3. Mycophenolate mofetil dose reduction (Secondary Outcome) – Defined as a reduction in dose of  $<1,500$  mg per day ( $<750$  mg PO BID). This will be assessed as a dichotomous outcome (yes/no) per patient as well as a rate (number of unique mycophenolate dose reduction events per patient-year). Events will be considered unique once the mycophenolate dose is returned to full dose for at least one week. The length of time a patient has their mycophenolate dose  $<1,500$  mg per day and the severity of mycophenolate dose reduction (nadir dose) will also be assessed. This endpoint will be measures at 3-, 6-, and 12-months post-transplant.

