If necessary, multivariable analysis assessments for Aims 1 and 2 will be conducted using Cox regression time to event models. The primary variable of interest in these models will be treatment (maribavir vs. valganciclovir). If necessary and appropriate given event rates, Cox regression analysis will also be used for survival analyses involving all time to event outcomes, including time to acute rejection, time to graft loss and time to death. Models will be adjusted for key variables known to influence outcomes, including CMV serostatus and rATG induction. To prevent overfitting, no more than one covariate for every 5 events will be included in these models. Given the small sample size and expected event rates, Cox models will likely be overfit if including >2 covariates plus the primary treatment variable. Thus, multivariable modeling will be limited to only include key baseline variables that are known to influence the risk of CMV infection and that significantly differ by treatment arm based on preliminary univariate analyses; this will most likely only include CMV D+/R- serostatus and/or rATG induction. Prior to conducting Cox regression, modeling assumptions will be assessed, including proportionality of hazards across treatment arms and assessing the optimal functional forms of non-dichotomous covariates.

For Aim 3, total hospital charges and healthcare utilization will be modeled using a validated method we have used in previous studies. This will be a two-part statistical models for zero-heavy continuous data. The general format of the suggested model in which we fit a logistic model for the probability of non-zero response and a conditional generalized linear model (GLM) for the mean response given that it is non-zero. We will consider several distributions for the GLM part (eg, log-normal, gamma and Weibull, zero-inflated negative binomial [ZINB]) and the best fitting model will be selected using Bayesian information criterion (BIC). Parameter estimates of percent change in total hospital charge per unit increase in the values of each covariate in the model and their 95% CI will be computed using SAS Proc FMM.

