#### **14.0 Withdrawal of Subjects**

Participation in this study is completely voluntary. Patients may withdraw at any time during the study. Treating physicians or providers may also request patients are withdrawn from the study if there are any safety concerns with participation. Patients that withdraw will be asked if they are willing to allow the data already collected on them to be included in analyses. Inclusion in the data analysis is also completely voluntary. If patients are agreeable, patient data will be censored at the time of withdrawal and these patients will be included in the intent-to-treat analyses.

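### Aim 3 models cumulative encounters and charges with no term for time observed, so unequal follow-up between arms would distort the comparison, though only slightly at the planned dropout

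*Combined protocol and SAP*

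**What the plan says.** Section 1.0 states a directional hypothesis for Aim 3: "Healthcare utilization will be lower in the maribavir arm, as compared to the valganciclovir arm, at 6- and 12-months post-transplant".

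Section 4.0, item 16, defines the outcome as a running record of use: "each encounter will be captured during the 12-month study and classified as hospitalizations, ED visits, ambulatory care visits", with further encounter types listed after these. It is assessed at 3, 6 and 12 months. The item adds that "Only MUSC encounters will be captured" and that "Charges will be converted to estimated costs using the Medicare Cost-to-Charge Ratio (CCR) for MUSC". It gives no rate and no denominator.

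Statistical Methods says that "total hospital charges and healthcare utilization will be modeled using a validated method we have used in previous studies". The model has two parts: "we fit a logistic model for the probability of non-zero response and a conditional generalized linear model (GLM) for the mean response", given that the response is non-zero. The distribution for the second part is chosen by BIC. No offset, exposure term, censoring weight or rule for partial follow-up is mentioned.

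Section 14.0 says of patients who withdraw and agree to the use of their data: "patient data will be censored at the time of withdrawal and these patients will be included in the intent-to-treat analyses". Section 6.0 does not replace patients who are lost or withdraw.

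By contrast, item 1 of the Safety Measures is analysed as yes/no "as well as a rate (number of unique leukopenia events per patient-year"), and items 2 to 5 have the same form.

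**The concern.** Censoring has a defined meaning in the Cox models planned for Aims 1 and 2. It has none in a two-part model of totals unless exposure is specified. As written, a patient who leaves at month 2 would contribute two months of encounters to a 12-month total. In the logistic part, an encounter type that the patient had not yet used would be scored as no use.

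There is a second route to the same problem. Because only encounters at the study institution count, a patient who moves care elsewhere records no further use even without a formal withdrawal.

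If both arms lose the same share of patients at the same times, the shortfall cancels from the ratio. If they do not, part of the difference in Aim 3 reflects observation time rather than treatment. The trial is open-label and Section 14.0 lets treating providers request withdrawal for safety concerns, so balance cannot be taken for granted. With 35 patients per arm, a few patients decide it.

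**Working it through.** **Inputs from the documents.** 35 patients per arm (Section 6.0); expected loss of 3-5% in each arm (Power/Sample Size); assessment at 3, 6 and 12 months (item 16).

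**Assumptions, because the documents give no figures.** Even use over the year; fraction of the year observed in leavers, *f*, between 0.1 and 0.5; for the simulations, a mean of 40 encounters per year with dispersion 0.5 or 0.3.

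**The plan's own figure.** Aim 3 has no sample size or effect size to reproduce. The primary calculation, which supplies the 35 and the 3-5%, does reproduce. At 33% versus 6%, two-sided 0.05 and 80% power, the chi-square formula gives 33 per arm against the stated 32. Then 32/0.97 = 33.0 and 32/0.95 = 33.7, so 35 covers the stated dropout.

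**Shortfall per leaver.** For *k* net extra leavers at month *m* in one arm, the 12-month mean falls by k/35 × (12 − m)/12. At m = 2:

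- k = 1: 1/35 × 10/12 = 2.4%
- k = 2: 4.8%
- k = 3: 7.1%

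If half the year's use fell by month 2 (an assumption), one leaver would cost 1/35 × 0.5 = 1.4%.

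**Ratio of arm means with no true difference.** With shares d_M and d_V lost in the maribavir and valganciclovir arms, ratio = [1 − d_M(1 − f)] / [1 − d_V(1 − f)].

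| Loss, maribavir vs valganciclovir | Apparent saving, f = 0.5 | Apparent saving, f = 0.1 |
|---|---|---|
| Equal | 0% | 0% |
| 5% vs 3% | 1.0% | 1.8% |
| 5% vs 0% | 2.5% | 4.5% |
| 15% vs 5% | 5.1% | 9.4% |
| 20% vs 5% | 7.7% | 14.1% |

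For example, 5% vs 3% at f = 0.1 gives 0.955/0.973 = 0.9815. Swapping the arms turns the saving into an apparent excess. Only the first two rows lie within the planned loss in both arms. In whole patients that means one or two per arm, so a net difference of at most one.

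**Effect of an offset.** Simulation with 35 per arm, dispersion 0.5 and leavers observed for a quarter of the year:

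| Leavers, maribavir vs valganciclovir | Ratio of totals | Ratio per person-time |
|---|---|---|
| 2 vs 2 | 1.003 | 1.003 |
| 2 vs 1 | 0.973 | 0.995 |
| 2 vs 0 | 0.959 | 1.002 |
| 5 vs 2 | 0.931 | 0.998 |
| 7 vs 2 | 0.891 | 1.004 |

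**Against sampling error.** With mean 40 and dispersion 0.5, the standard error of the log ratio is √[2/35 × (1/40 + 0.5)] = 0.173. A bias of 1.0-1.8% is 0.010-0.019 on the log scale, or about 0.06-0.11 standard errors.

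**False positives.** With dispersion 0.3, month-2 leavers and no offset, 2,000 simulated trials per setting rejected in 5.8% with no leavers, 3.6% with two versus one, 3.5% with two versus two and 5.4% with two versus none. The Monte Carlo standard error at 5% is √(0.05 × 0.95/2000) = 0.5 points. None of the settings with leavers is clearly above 5%.

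**The case against.** The strongest reply is that the plan expects the same 3-5% loss in each arm. On that expectation the bias is nil to about 2%, far inside sampling error. This stands, and it sets the size of the point.

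Other objections also stand in part:

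- **Poor tolerability.** A reader might infer that the worse-tolerated arm would automatically be credited with a saving. The documents do not support this. Section 6.0 keeps patients taken off study drug in the study, and encounters come from the institution's own records without study-only visits. Stopping the drug therefore does not shorten follow-up. Only withdrawal from the study, or leaving the institution's care, does.
- **Refusal of data use.** Patients who withdraw and decline the use of their data are not analysed, so they do not count as low users.
- **Direction.** If use is concentrated early, the shortfall shrinks. The assessment schedule is itself dense in the first month. If leavers were heavy users before leaving, the direction can reverse.
- **Cited method.** Statistical Methods refers to an earlier published application of the model, which may have handled exposure. That cannot be checked here, and the citation does not say how this trial will treat partial follow-up.

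None of this supplies the missing rule. The 3-5% is a forecast, and choosing a method after losses by arm are visible in an open-label trial would invite a data-driven choice.

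**Conclusion.** The gap is real. Aim 3 models totals, consenting withdrawn patients stay in with truncated data, and nothing brings in the time observed, although items 1 to 5 also report patient-year rates.

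Other things equal, the arm with less follow-up looks lower-using, by about 2.4% of its 12-month mean for each net extra patient leaving at month 2. That figure rests on even use over the year and is smaller if use comes early. At the planned loss the bias is about 0-2%. It reaches about 5-14% only if one arm loses 15-20% and the other 5%, which is well outside the plan.

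A reader might infer that Aim 3 is likely to show a false saving for maribavir, or that its type I error is inflated. Neither is established. The documents give no reason to expect more loss in one arm, and the simulations show no detectable inflation at planned loss. Severity is modest: the aim is secondary and the primary analysis is unaffected.

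**What to change.** In the Aim 3 paragraph of Statistical Methods:

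1. **Counts.** Model encounters in the intervals 0-3, 3-6 and 6-12 months, which follow the plan's own assessment times, with log(days observed in the interval) as an offset. A patient contributes only intervals with at least one observed day, so log(0) does not arise. Allow for repeated intervals within a patient in the standard errors.
2. **Any use.** Bring observed time into the first part too, for example with a complementary log-log link and the same offset: log(−log(1 − p)) = linear predictor + log(days).
3. **Charges.** Estimate the mean in each interval among patients still under observation and sum over intervals, with a stated rule for partly observed intervals.
4. **Censoring and death.** Treat withdrawal and the end of follow-up at the institution as censoring, and record the date of each. Count patients who die over the full window and report deaths alongside.
5. **Reporting.** Give follow-up time by arm next to the Aim 3 results.

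The cost is SAP wording, modest programming and a recorded end-of-follow-up date, including for patients who move care without formally withdrawing. Confidence intervals widen slightly. The method assumes that, within an interval, leaving is unrelated to later use. It therefore corrects for unequal time but does not remove bias from informative withdrawal.
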